**Appendix 1: Numerical Pain Scale NRS on Walking for Joint Pain****INSTRUCTIONS**

1. Place an "X" in the box below that indicates the amount of pain the subject feels in joint on walking on a flat surface in the last 24 hours.
2. Complete for the following joints:

Index	Contralateral
Hip	Hip
Knee	Knee
Ankle	Ankle

0	1	2	3	4	5	6	7	8	9	10	
No Pain	Mild			Moderate			Severe			Worst Pain	

## Appendix 2 American Orthopedic Foot and Ankle Score AOFAS

### Ankle-Hindfoot Scale (100points Total)

**I Pain (40 points)**

None	40
Mild, occasional	30
Moderate, daily	20
Severe, almost always present	0

**II Function (50 points)**

Activity limitations, support requirement	
No limitations, no support	10
No limitation of daily activities, limitation of recreational activities, no support	7
Limited daily and recreational activities, cane	4
Severe limitation of daily and recreational activities, walker, crutches, wheelchair, brace	0

Maximum walking distance, blocks	
Greater than 6	5
4-6	4
1-3	2
Less than 1	0

Walking surfaces	
No difficulty on any surface	5
Some difficulty on uneven terrain, stairs, inclines, ladders	3
Severe difficulty on uneven terrain, stairs, inclines, ladders	0

Gait abnormality	
None, slight	8
Obvious	4
Marked	0

Sagittal motion (flexion plus extension)	
Normal or mild restriction (30° or more)	8
Moderate restriction (15°-29°)	4
Severe restriction (less than 15°)	0

Hindfoot motion (inversion plus eversion)	
Normal or mild restriction (75%-100% normal)	6
Moderate restriction (25%-74% normal)	3
Marked restriction (less than 25% normal)	0

Ankle-hindfoot stability (anteroposterior, varus-valgus)	
Stable	8
Definitely unstable	0

**III Alignment (10 points)**

Good, plantigrade foot, midfoot well aligned	15
Fair, plantigrade foot, some degree of midfoot malalignment observed, no symptoms	8
Poor, nonplantigrade foot, severe malalignment, symptoms	0

Total=100

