Criteria for Evaluation	
Primary Endpoint:
 
 
Reduction of index joint Numerical Rating Scale (NRS) pain on walking from baseline to 6 Months post injection.
 
 
Secondary Endpoints:
 
 
Improvement in AOFAS index from baseline to 6 months post injection.
 
Improvement in Patient Global Assessment (PGA) from baseline to 6 months post injection.
 
OMERACT-OARSI responder rate in the index joint at 6 months post injection.
 
Time to treatment failure
 
Reduction in Medication usage from baseline to 6 months post injection.
 
 
Exploratory Endpoints
 
Any comparisons across timepoints (baseline to 6 months) not described in the primary or secondary endpoints including but not limited to:
 
 
Demographics
 
Medical History
 
History of joint osteoarthritis
 

	
 
• Rescue Medication Use
 
• Treatment Failure
 
• Injection procedure
 
• Concomitant medications
 
• Non-drug therapy
 
 
Safety Endpoint:
 
The incidence, severity, and relationship to treatment of all Adverse Events (AE) will be collected from the first treatment injection to the 6 month assessment.

Statistical Analysis	
The primary analysis on the endpoints will be performed on the ITT (Intent to Treat) populations. All Primary and Secondary endpoints will be analyzed using the ITT population.
 
A secondary analysis will be conducted on the Per Protocol (PP) population. Since the primary endpoint is at 6 months this is all subjects who complete the 6 month assessment and do not have a major deviation in the conduct of the protocol. For all other visits, this is defined as the subjects who complete those visits according to the protocol.
 
All safety analyses will be conducted on all subjects who undergo treatment of MONOVISC in the ankle joint.

Sites	Up to 20 clinical sites in EU
Sponsor	
Anika Therapeutics, Inc.  [name],  United States of America  Phone: + 1 [contact] Fax: + 1 [contact]

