### 6.2 Secondary Endpoints:

- Improvement in AOFAS index joint from baseline to 6 months post injection.
- Improvement in Patient Global Assessment (PGA) from baseline to 6 months post injection.
- OMERACT-OARSI in the index joint responder rate at 6 months post injection.
- Time to treatment failure
- Reduction in Medication usage from baseline to 6 months post injection.

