## 7. STUDY PROCEDURES

### 7.1 Schedule of Events

Assessments	Screening Visit Day -14 to -7 ±2 days	Baseline Visit Day 0	Month 1 Visit	Month 3 Visit	Month 6 Visit
			±3 days	± 7 days	± 7 days
Informed Consent	X				
Evaluation of Enrollment Criteria	X	X			
Demographics	X				
Vital Signs	X				
History Joint OA (Index & Contralateral for hip, knee and ankle)	X				
Medical History	X				
Concomitant Medication	X	X	X	X	X
Assess non-drug therapies	X	X	X	X	X
Adverse Event Assessment		X	X	X	X
Collect & Review Subject Diary		X	X	X	X
Rescue Medication usage / washout		X	X	X	X
Patient Global Assessment (PGA)	X	X	X	X	X
AOFAS index for index and contralateral ankle	X	X	X	X	X
Index and Contralateral Joints Pain (0-10 Numeric Rating Scale) for Hip, Knee and Ankle joints	X	X	X	X	X
Physical Evaluation of Index and Contralateral Joints for Hip, Knee and Ankle joints	X	X	X	X	X
Study Injection		X			
Dispense Subject Diary		X			

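### The AOFAS form gives 15 points to the best option of an alignment item headed 10 points, so the scale behind a secondary endpoint adds to 105, not the stated 100

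*Protocol*

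**What the plan says.** The endpoint is listed in Protocol Section 6.2 as "Improvement in AOFAS index joint from baseline to 6 months post injection" and in the Section 2 synopsis as "Improvement in AOFAS index from baseline to 6 months post injection". The Section 7.1 schedule has the row "AOFAS index for index and contralateral ankle" marked at all five visits, from screening to month 6.

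Appendix 2 holds the scoring form. It opens with "Ankle-Hindfoot Scale (100points Total" and closes by giving the total as 100 again. It has three sections, headed 40 points for pain ("I Pain (40 points"), 50 for function and 10 for alignment ("III Alignment (10 points"). The alignment options are:

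- "Good, plantigrade foot, midfoot well aligned": 15
- "Fair, plantigrade foot, some degree of midfoot malalignment observed, no symptoms": 8
- Poor: 0

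**The concern.** An item worth at most 10 points cannot award 15. The form therefore contradicts its own section heading and both of its stated totals, and it is the only AOFAS scoring rule in the protocol.

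Three things are at stake for the secondary endpoint:

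- **Level.** Scored as printed, an ankle rated Good gets 5 points more than the heading allows, and a score described as out of 100 can reach 105.
- **Change.** Moves into or out of Good carry a different weight from the one a 10-point item gives them.
- **Consistency.** A rater who sees a 10-point heading and a 15-point option could reasonably record either, and Section 6.5 allows up to 20 sites. If one visit uses 15 and another uses 10, a subject whose foot has not changed shows a 5-point change. The protocol does not show whether this happened.

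**Working it through.** **Inputs.** All are best-option scores and headings from Appendix 2. The subject number, 25, is from Sections 2 and 9.1.

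**Step 1: the stated total.** Section headings: 40 + 50 + 10 = 100. This reproduces the total given at the top and foot of the form.

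**Step 2: the printed options.**

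| Section | Best options | Sum | Heading |
|---|---|---|---|
| Pain | 40 | 40 | 40 |
| Function | 10 + 5 + 5 + 8 + 8 + 6 + 8 | 50 | 50 |
| Alignment | 15 | 15 | 10 |
| Total | 40 + 50 + 15 | **105** | 100 |

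The whole excess, 105 − 100 = 5, comes from the alignment item. With a best score of 10 the form gives 40 + 50 + 10 = 100 and agrees with all three headings and both totals.

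**Step 3: effect on the change score.** The change in the item is its score at 6 months minus its score at baseline. The comparison sets Good at 10 and leaves Fair at 8 and Poor at 0.

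| Move | As printed | Good = 10 | Difference |
|---|---|---|---|
| Same category | 0 | 0 | 0 |
| Poor to Fair | +8 | +8 | 0 |
| Fair to Good | 15 − 8 = +7 | 10 − 8 = +2 | +5 |
| Poor to Good | +15 | +10 | +5 |
| Good to Fair | −7 | −2 | −5 |
| Good to Poor | −15 | −10 | −5 |

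The rows involving Fair depend on Fair = 8 being correct, which the protocol does not establish. The Poor/Good rows do not depend on it.

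**Step 4: effect on the mean change.** With m net moves into Good among 25 subjects, the shift is 5m/25 = 0.2m points.

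| Net moves into Good (m) | Shift in mean change |
|---|---|
| 0 | 0 |
| 1 | 0.2 |
| 3 | 0.6 |
| 5 | 1.0 |

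The protocol gives no rate for such moves. The range of 0 to 5 is an assumption, used only to show scale.

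**The case against.** The arithmetic is not in dispute. The case on the other side is that the consequences may be small or nil.

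- **The CRF is not shown.** Section 10.1 has data entered on CRFs, and the CRF or a statistical analysis plan may already score Good as 10. This stands: the 5-point excess applies only if forms are scored as printed. It does not excuse a protocol form that contradicts itself.
- **The excess often cancels.** Alignment describes foot position, and one injection for symptom relief may rarely change it. This also stands as a limit on size. Movement is still possible, because the option wording refers to symptoms, and the only deformity exclusion (Section 6.6.2, criterion 15) concerns the knee, so feet rated Fair or Poor can be enrolled.
- **The illustrated range is arbitrary.** Five net moves would be 20% of 25 subjects, all in one direction. What is firm is 0.2 points per net move, with the number of moves unknown.
- **Fair = 8 is unverified.** Correct, and the entries that use it are conditional.
- **The reach is limited.** The study has a single arm, so no between-group comparison is affected. AOFAS is one of five secondary endpoints. The primary endpoint, NRS pain on walking, and the sample size built on it do not use this form.

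These points keep the finding from being graded higher. None removes the contradiction.

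**Conclusion.** The form is wrong as written: its options add to 105 and it states 100. The heading and both totals agree with each other, so the printed 15 is the likely error. Whether Fair = 8 is also wrong cannot be told from the protocol.

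If scored as printed, levels are 5 points too high for each ankle rated Good, relative to a 10-point item. The change score shifts by 5 points for a move between Poor and Good, and by the same amount between Fair and Good if Fair stays at 8. It does not shift when the category is unchanged and the same scoring is used at both visits. The effect on the mean change is probably small, but the endpoint should not be reported on a scale whose maximum is undefined. This should be fixed before analysis.

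**What to change.** Check all three alignment scores against the source instrument, so that the item fits its 10-point heading and the form totals 100. Good = 10 is the only top value that does this; Fair = 8 needs its own check. Then issue one corrected form and score every visit, baseline included, with the same values.

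Forms already completed should be re-scored from the recorded alignment category. If only points or a total were stored, the category has to be taken from the source form.

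The cost is one corrected appendix page, documented as an amendment under Section 13.3 if ethics approval has already been given. Re-scoring is a recalculation if the CRF stores the category; otherwise it needs a source check for each completed form. No change is needed to the design, the sample size or the primary analysis.

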**Appendix 3 Patient Global Assessment**

To be assessed by the Subject as the first questionnaire.

The pain the subject felt in INDEX joint caused by osteoarthritis during the last 24 hours.

Have the Subject record their response with an "X":

Think about the pain you felt in your STUDY ankle caused by your osteoarthritis during the last 24 hours.

"Considering all the ways the osteoarthritis in your STUDY ankle affects you, what is your assessment of how much your STUDY ankle is bothering you today?"

0	1	2	3	4	5	6	7	8	9	10
No Pain	Mild			Moderate			Severe			Worst Pain
